This study will include patients age 7 years or older with mutations in *RYR1* (confirmed by previous genetic testing), who are not currently taking antioxidants, and who are able and willing to perform all procedures at the time of enrollment. Children under age 7 may not be

able to successfully follow instructions for outcome measure testing. The accrual ceiling is 100. Withdrawals/dropouts will not be replaced. The target number of completers is 76.

Sixty to 100 age-matched healthy volunteers will be recruited.

NIH employees may participate. The NIH Information Sheet on Staff Research Participation will be provided to any staff member wishing to participate in this study (see Appendix L).

b. Inclusion criteria

Patients:

- Have a confirmed genetic diagnosis of RYR1-related myopathy, including congenital myopathy, OR have a clinical diagnosis of RYR1-related myopathy and a family member with a confirmed genetic diagnosis of RYR1-related myopathy
- Ambulatory.
- 7 years of age or older.
- Preferred: The affected subject has a previous muscle biopsy with available report confirming RYR1-related myopathy histopathology.

Healthy Volunteers:

- Ages 7 and older (15-25 7-12 year olds, 15-25 13-17 year olds, 15-25 18-40 year olds, 15-25 41 and older) without medical condition resulting in or complaints of muscle weakness and/or fatigue.
- The ability to provide consent.

c. Exclusion criteria

Patients:

- Adults who cannot provide their own consent and pediatric participants who do not have a parent able to provide consent
- Patients with a history of liver disease (Liver Function Tests will be collected at baseline and at each study visit as a precautionary measure). Liver disease is defined as moderate to severe hepatic impairment based on the following:
ALT \geq 8x upper limit of normal (ULN) with total bilirubin 2x ULN (plus >35% 'direct' bilirubin) and/or INR >1.5
or
GGT > 2-3x ULN with bilirubin 2x ULN (plus >35% 'direct' bilirubin) and/or INR >1.5
GGT >2-3x ULN and INR >1.5
- Patients with a history of peptic ulcers, gag reflex depression, and esophageal varices. Patients with gastrostomy tubes may be considered for participation, in the case of gag reflex depression or other swallowing or feeding difficulties.

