- Patients who have a severe pulmonary dysfunction (FEV1 < 40% predicted) or evidence of pulmonary exacerbation. Pulmonary exacerbations refer to an acute worsening of respiratory symptoms that result from a decline in lung function (Flume et al., 2009). Participants may present with increased coughing, increased dyspnea, increased haemoptysis, increased fatigue, decreased pulmonary function by a min of 10%, or a change in sputum color (Bilton et al., 2011).
- Pregnant and breastfeeding women.
- Consumption of antioxidants [including NAC, GSH, melatonin, Immunocal (Immunotac

Research, Vandreuil-Dorion, QC, Canada), Nacystelyn (Galephar, Brussels)] in the 4 weeks before recruitment.

- Daily use of acetaminophen (including Percocet, Vicodin, Oxycodone, Excedrin, and other acetaminophen-containing drugs), nitroglycerine, or carbamazepine during the past 7 days.
- Current use of Angiotensin-converting enzyme (ACE) inhibitors or Angiotensin Receptor Blockers (ARBs)
- Patients who have ever used Beta2-adrenergic agonist tablets, for the purpose of increasing muscle mass (such as albuterol tablets).
- For the muscle biopsy procedure only (second and third visits, if applicable): Patients who have taken Aspirin, Ibuprofen, Advil, Motrin, or Aleve within the 3 days prior to the muscle biopsy procedure, and/or patients who have taken Plavix, fresh garlic, ginkgo, or ginseng 5 days prior to the muscle biopsy.
- Participation in trials for other therapeutic investigational drugs simultaneously or 4 weeks before recruitment.

Other clinically significant medical disease that, in the judgment of the investigators, would expose the patient to undue risk of harm or prevent the patient from completing the study. Examples include anemia (defined as Hgb < 8 gm/dl), an inability to walk safely without assistance for at least 6 minutes, and/or an inability to consume at least 6 ounces of fluid, 3 times a day, either orally or via G-tube. Patients with comorbidities (i.e. cancer, epilepsy) will be carefully assessed to determine if their comorbidity could lead to confounding or safety issues, should their participation continue.

Healthy Volunteers:

- Diagnosis of RYR1-related myopathy or other neurological disorder (by neurological exam, genetic testing, or muscle biopsy)
- Complaints of fatigue or weakness
- Consumption of antioxidants [including NAC, GSH, melatonin, Immunocal (Immunotac

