“Central Core Disease & Minicore: a place for support, learning & friends”, which is found at this link: <https://www.facebook.com/groups/243087794204/>. We will also tweet our study at <https://twitter.com/NINR> and use the web slide carousel on the NINR website

<https://www.ninr.nih.gov/researchandfunding/dir#.VzzUSRIrKRs>, to advertise our study.

A telephone or email prescreening will be used to determine preliminary eligibility (prescreen questionnaire, Appendix G). The prescreening telephone call will be scheduled or the prescreen questions will be sent via email. During the prescreening phase, we will request the potential participant send the results of their genetic testing confirming diagnosis of RYR1 (if done) and the results of their muscle biopsy confirming RYR1 histopathology (if done). We will receive these documents via mail, fax, or secure email before their visit. This will prevent patients who are clearly not eligible from making an unnecessary trip to NIH. The records of any participant who subsequently does not qualify will be destroyed or returned to the participant.

We will not request records of relatives of participants/potential participants who are enrolling under the criteria of a clinical diagnosis with a family member with confirmed RYR1.

There is no direct solicitation of employees/staff by supervisors. Direct solicitation by co-workers is considered improper.

c. Screening

Patients:

Informed consent will be obtained before any study procedures begin. We will screen participants by determining whether or not they meet inclusion/exclusion criteria by using the eligibility checklist (Appendix E).

At the onset of the study, individuals will be required to have a documented muscle biopsy confirming RYR1 diagnosis. If 20 individuals with this documentation cannot be recruited within the first 6 months, those without muscle biopsy confirmation will also be enrolled.

Healthy Volunteers:

Healthy volunteers will be screened by phone, email, or in-person for the presence of any neurological condition and/or complaints of weakness and fatigue and will be asked about current medications, per the eligibility criteria.

d. Study procedures

Patients:

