When administered as oral effervescent tablets, NAC has few severe side effects, providing a favorable risk benefit ratio to the proposed trial (Tirouvanziam et al, 2006; Hardan et al., 2012). Side effects of PharmaNAC effervescent tablets, which we plan to administer, include diarrhea, nausea, abdominal pain, vomiting, constipation, and flatulence, particularly when used chronically in high doses up to 6.9g/day. The dosage (2700mg/day) for our study is within the

range of dosages previously used in clinical trials and is considered high. If the participants, at any point in the study, should need to take antibiotics, they will be informed to take their antibiotic medication (penicillins, tetracyclines, cephalosporins, and aminoglycosides) at least two hours prior to taking NAC. Other drugs that interact with NAC and GSH include, nitroglycerine, carbamazepine for NAC, and acetaminophen for GSH. Use of these medications is exclusionary, and participants cannot have taken them within seven days of the start of the study. Participants will not stop taking prescription medications for the purposes of this study unless they can be safely discontinued. In this case, the discontinuation will be done under the care of the prescribing physician. It is important to note that high levels of NAC administration have not been tested in pregnant or lactating women, therefore, pregnancy is an exclusion criteria. As mentioned previously, if women become pregnant during this study, we will follow up with these women during their pregnancy and at birth.

Side effects reported when NAC is inhaled or injected include rhinorrhea, stomatitis, generalized urticarial/ facial flushing, rash, pruritis, headache, drowsiness, clamminess, chest tightness, bronchoconstriction, and hypotension. Anaphylaxis is a rare but possible side effect in IV administered NAC in response to acetaminophen overdose. However, we will not be administering NAC in the inhaled or IV routes, and there have been no reports of anaphylaxis with oral administration.

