In our proposed study, after participants receive drug or placebo effervescent tablets at the 6-month visit, they will be monitored at NIH for 2 consecutive days as an extra precaution to rule out rhinorrhea, stomatitis, urticarial/ facial flushing, rash, pruritus, hives, coughing, headache, drowsiness, clamminess, chest tightness, bronchoconstriction, and hypotension, which are the most severe potential side effects of inhaled or injected NAC. This monitoring will include being observed in the outpatient clinic for 2 hours after their initial dose, including having vitals signs measured. The second day of observation at NIH will include an outpatient clinic visit with vital signs. If at any other time, the participant notices any symptoms, they will be directed to contact our onsite nurses. A Licensed Care Provider will then call them at one and three weeks to monitor adverse reactions. We will then monitor participants monthly (2, 3, 4, and 5 months) by phone and/or email, primarily for gastrointestinal symptoms, which are the main symptoms of PharmaNAC effervescent tablets. If a patient reports any of the side effects that have already been reported (rash, chest tightness with coughing, hives, or hypotension), they will be advised to stop taking the study medication immediately. They will only restart the study medication after discussing their symptoms with the PI. Patients are also asked, in the consent form, to limit their alcohol consumption to no more than 2 alcoholic drinks per day as excess alcohol consumption may interact with glutathione levels. Participants are informed to call study investigators immediately if they have any problems or side effects and are provided with contact information. They are instructed to visit the emergency room if they have a possible allergic reaction or a serious or life-threatening emergency. They are expected to tell the ER staff that they are in a research study and ask the emergency personnel call the research nurse. Participants are instructed to continue under the care of their local clinicians throughout participation. Participants are provided with a “NAC Information Letter for Clinicians” (Appendix F) to share with their home clinicians. This letter provides study drug information and information about possible side effects.

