There will be no difference in mean corrected 15-F2t-isoprostane concentration or 6MWT distance, between the *RYR1*-RM and otherwise healthy individuals.

Alternative Hypothesis (H_1)

Corrected 15-F2t-isoprostane concentration will be significantly increased and 6MWT total distance will be significantly decreased in *RYR1*-RM myopathy patients when compared to otherwise healthy individuals.

2. After 30 participants complete their 2nd visit at 6 months (prior to starting study drug/placebo), disease progression will be assessed using paired t-tests to determine changes between 0 and 6-month visits for each outcome measure. For the primary outcome measures (corrected 15-F2t-isoprostane concentration and 6MWT) change between 0 and 6-month time points will be assessed. This analysis will be repeated when all 6-month visits are completed.

Null Hypothesis (H₀)

Corrected 15-F2t-isoprostane concentration and 6MWT total distance will not change significantly between 0 and 6 months in *RYR1*-RM myopathy patients.

Alternative Hypothesis (H₁)

There will be a statistically significant difference between 0 and 6-month values for corrected 15-F2t-isoprostane concentration and/or 6MWT total distance in *RYR1*-RM myopathy patients.

Intervention phase analyses (month 6 to month 12)

- Use an independent t-test (or non-parametric equivalent) to compare pre-intervention (month 6) values for demographics, urine isoprostane and six-minute walk test between NAC versus placebo groups.
- Using multiple imputation (x40 datasets and minimum/maximum value constraints from *per protocol* data) impute missing month 12 data.
- The following GLM should be run both *per protocol* and with ITT datasets.
 1. Run a general linear model comparing month 12 month corrected 15-F2t-isoprostane concentration (corrected_f2-isop_month12, corrected_f2-isop_PGF2alpha_ratio_month12) between NAC and placebo groups controlling for pre-intervention value. Run this model again controlling for established *a priori* confounders including age, sex, height, weight, BMI, smoking status, alcohol status. Variables that do not contribute significantly to the model may be removed. (Exclude RYR023, RYR024, and all healthy volunteers).

Null Hypothesis (H₀)

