2. UP/SAE
3. Non-UP/SAE

The other categories do not apply as they are not AEs.

Please use these categories in column F: "IRB determination of category".

Exclude HVs (healthy volunteers) and only use RYR numbers. Exclude RYR023 and RYR024.

For the remaining AE events (i.e. in the 3 categories delineated above) all have individual RYR IDs.

Assess:

1. Which AEs occurred in NAC group and which occurred in Placebo group (descriptive statistics) (see attached p.1 Mock Table 1)

2. Were there more specific AEs (by preferred term, Column H on excel) of any kind in NAC vs. Placebo groups? Or were AEs equally distributed between groups? Both Chi-square test and Fisher's exact test extended to general RxC tables, aka the Freeman-Halton test, will be used to compare AE frequencies between NAC and Placebo groups.
3. For those in NAC group, what was event causality (see AE excel column Q) and what was event severity (AE excel column R)? (for an example of this table, see p. 7 of attached, first table on p. 7). Capture the "body system" from our AE excel column G (AKA "system organ class").

Secondary Outcome Measures

Natural History Phase (month 0 to month 6):

Aim 1: plasma GSH:GSSG ratio; plasma CYS:CYSS ratio, (corrected DCF-fluorescence intensity (month 6 only))

1. We will compare baseline outcome measure values against healthy controls, when possible, using a summary independent t-test (or non-parametric equivalent). Hedge's g will be used to assess standardized mean differences between *RYR1*-RM and otherwise healthy population groups.

Null Hypothesis (H_0)

There will be no difference in mean plasma GSH:GSSG ratio; plasma CYS:CYSS ratio, or corrected DCF-fluorescence intensity, between *RYR1*-RM and otherwise healthy individuals.

Alternative Hypothesis (H_1)

Plasma GSH:GSSG, and CYS:CYSS ratios will be significantly decreased and corrected DCF-fluorescence intensity will be significantly increased in *RYR1*-RM myopathy patients when compared to otherwise healthy individuals.

2. We will compare baseline outcome measure values against values obtained at month 6 using paired t-tests (or non-parametric equivalent) to determine changes between 0 and 6-month visits for each outcome measure.

Null Hypothesis (H_0)

Plasma GSH:GSSG, and CYS:CYSS ratios and corrected DCF-fluorescence intensity will not change significantly between 0 and 6 months in *RYR1*-RM myopathy patients.

Alternative Hypothesis (H_1)

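### Daily acetaminophen users can serve as healthy glutathione references although patients taking it are excluded, and comparisons with the trial's own volunteers adjust for age at most

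*Protocol*

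**What the plan says.** **Volunteer eligibility (Protocol 3.b, 3.c).** Volunteers must be "without medical condition resulting in or complaints of muscle weakness and/or fatigue". They are excluded for RYR1-related myopathy or another neurological disorder, for fatigue or weakness, for antioxidants in the preceding 4 weeks, and for beta2-agonists. The list ends there.

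**Volunteer screening (Protocol 4.c).** "Healthy volunteers will be screened by phone, email, or in-person for the presence of any neurological condition and/or complaints of weakness and fatigue". The sentence goes on to say that current medications are asked about, with reference to the eligibility criteria.

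**Patient eligibility (Protocol 3.c).** Patients have the same antioxidant rule and, among others, this exclusion: "Daily use of acetaminophen (including Percocet, Vicodin, Oxycodone, Excedrin, and other acetaminophen-containing drugs), nitroglycerine, or carbamazepine during the past 7 days".

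**Reasons given (Protocol 7).** "Other drugs that interact with NAC and GSH include, nitroglycerine, carbamazepine for NAC, and acetaminophen for GSH". Patients are also asked, in their consent form, to limit alcohol because "excess alcohol consumption may interact with glutathione levels".

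**Use of the volunteers.** Aim 3 takes volunteer biomarkers as normal values. Protocol 10 (Healthy volunteer data) plans an age-matched comparison with patients at alpha 0.05. For the redox ratios the SAP (Secondary Outcome Measures, Natural History Phase, Aim 1) says: "We will compare baseline outcome measure values against healthy controls, when possible, using a summary independent t-test", with Hedges' g alongside.

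**Confounders named.** For the month-12 isoprostane model comparing NAC with placebo, the SAP lists "confounders including age, sex, height, weight, BMI, smoking status, alcohol status". That model leaves out all volunteers.

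**The concern.** A reference group should be free of the exposures that the investigators themselves link to the biomarker. Repeating the antioxidant rule for volunteers shows that the authors saw this need. The acetaminophen rule was not repeated, although acetaminophen is the one other barred drug that the protocol ties to glutathione. The medication question does not close the gap, because the criteria it refers to give no ground for excluding an acetaminophen user.

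The analysis does not make up for this. Volunteer quotas and matching use age only, and the SAP's t-test carries no covariates, although the SAP regards sex, BMI, smoking and alcohol as confounders of isoprostane elsewhere. A shift in volunteers towards patient values would hide a real patient deficit, and a shift the other way would exaggerate one. The Aim 3 normal values would carry the same distortion.

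**Working it through.** **1. Criteria side by side**

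| Item | Patients | Volunteers | Reason in the documents |
|---|---|---|---|
| Antioxidants, 4 weeks | excluded | excluded | list names NAC and GSH themselves |
| Daily acetaminophen, 7 days | excluded | no rule | interacts with GSH |
| Nitroglycerine, carbamazepine | excluded | no rule | interact with NAC, which volunteers do not take |
| ACE inhibitors/ARBs | excluded | no rule | none given |
| Liver disease | excluded | no rule, but liver tests are drawn | no biomarker reason |
| Pregnancy, breastfeeding | excluded | no rule | high-level NAC untested in these women |
| Alcohol | asked to limit | nothing seen | may interact with glutathione |
| Smoking | no rule | no rule | covariate in the randomized isoprostane model |

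Only the acetaminophen and alcohol rows show both a difference between the groups and a stated link to glutathione.

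**2. What is recorded for volunteers.** Protocol 4.d (Healthy Volunteers) lists a physical examination with height, weight and BMI, plus blood, saliva, urine, NIRS, ultrasound and MRI. It lists no medical, smoking or alcohol history. Patients do give a medical history.

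**3. Which comparisons are exposed.** Exposed: the age-matched biomarker analysis in Protocol 10, the Aim 3 values, and the SAP's redox ratios wherever the trial's own volunteers are the comparator. Not exposed: the NAC-placebo models, and the SAP's primary isoprostane comparison, which uses existing healthy data.

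**4. Size, as an illustration.** The plan gives no sample size or effect for the patient-volunteer comparison. Its one derived figure, 38 per group, concerns the change in GSH on NAC versus control. That figure reproduces (Satterthwaite power 0.798 at 37 and 0.809 at 38, from delta 1.7 and SDs 2.34 and 2.80) but does not bear on this point.

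Assumptions: a share p of volunteers is exposed, no patients are (true by rule for daily acetaminophen), and exposure moves the biomarker by s SD towards patient values. Neither p nor s is in the documents.

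- Bias = p × s.
- Volunteer variance = 1 + p(1 − p)s².
- SE = √(1/n₁ + variance/n₂), two-sided Welch test at 0.05, noncentral t.
- True difference set to give 80% power without bias: 0.637 SD for 30 patients (first look) and 60 volunteers; 0.429 SD for 76 (target completers) and 100.

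Worked case, p = 0.10 and s = 0.5. Bias = 0.05 SD. Variance = 1 + 0.10 × 0.90 × 0.25 = 1.0225.
- 30 vs 60: SE = √(1/30 + 1.0225/60) = 0.224; (0.637 − 0.05)/0.224 = 2.62; power 73%.
- 76 vs 100: SE = √(1/76 + 1.0225/100) = 0.153; (0.429 − 0.05)/0.153 = 2.48; power 69%.

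| p | s (SD) | Bias (SD) | Power, 30 vs 60 | Power, 76 vs 100 |
|---|---|---|---|---|
| 5% | 0.25 | 0.013 | 78% | 78% |
| 10% | 0.5 | 0.05 | 73% | 69% |
| 20% | 0.5 | 0.10 | 65% | 57% |
| 20% | 1.0 | 0.20 | 47% | 30% |
| 30% | 1.0 | 0.30 | 30% | 13% |

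Two of the four equal age quotas are children. If only adults are exposed, 10% overall means 0.10/0.5 = 20% of adults, and 30% overall means 60%. The lower rows are therefore outer bounds. For smoking and alcohol, which patients may share, the bias is (p in volunteers − p in patients) × s and may be zero.

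**The case against.** Much can be said on the other side, and several stronger readings fail.

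- **A reader might infer that every patient drug and disease exclusion should apply to volunteers.** The documents do not support this. Nitroglycerine and carbamazepine are tied to NAC, pregnancy to untested NAC exposure, and no biomarker reason is given for ACE inhibitors/ARBs or liver disease.
- **A reader might infer that smoking and alcohol are controlled in patients but not in volunteers.** That is wrong for this comparison. The adjustment belongs to the randomized models, no patient is excluded for either, and neither side is adjusted when patients are compared with healthy people.
- **A reader might infer that the primary isoprostane comparison is compromised.** The SAP makes that comparison against existing data, and the protocol cites a set of 1881 healthy people.
- **A reader might infer that volunteers have no covariates at all.** Age is known from the quotas, and height, weight and BMI may be taken.
- **The protocol speaks of interaction only.** It gives no direction or size, and it does not say that any barred drug moves isoprostane.
- **Absence is not proven.** The eligibility checklist, prescreen questionnaire and volunteer consent form were not available. The SAP's data files include smoking and alcohol variables that might cover volunteers.
- **The stakes are limited.** GSH lost its primary role because of assay problems, the SAP describes plasma redox only if possible, and the healthy comparison is made only when possible. The study is closed to data analysis.

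All of this stands, and it narrows the point. It does not remove the missing acetaminophen rule or the lack of adjustment beyond age in a planned comparison.

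**Conclusion.** The point holds in a limited form. The volunteer criteria omit the one further drug exclusion that the protocol links to glutathione, the listed volunteer procedures capture no medical, smoking or alcohol history, and the comparison with the trial's own volunteers is adjusted for age at most. Bias in the patient-versus-volunteer GSH and other biomarker comparisons, and in the Aim 3 values, is possible. Its direction and size cannot be read from the documents. The range above, 0.013 to 0.30 SD, rests wholly on assumed exposure and shift, and its upper end needs an exposure share that looks extreme for a group that is half children. The randomized NAC-placebo result is not touched. This is a cheap improvement to a secondary, natural-history comparison, and only its analytic part can still be applied.

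**What to change.** 1. State for each biomarker whether the healthy comparator is the trial's own volunteers or existing data.
2. Where it is the trial's own volunteers, replace the unadjusted t-test by a linear model of group with age, sex and BMI. Add smoking and alcohol if they were recorded for volunteers.
3. Repeat the glutathione comparison without volunteers whose screening medication answers show daily acetaminophen use. If those answers were not kept, state the limitation.
4. For a future study, or had enrolment here been open: apply the acetaminophen exclusion to volunteers, and record smoking, alcohol and medication at their single visit.

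The cost is one extra model and one table, with a slightly smaller reference group in the sensitivity analysis. Step 1 takes a sentence per biomarker.

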Muscle biopsy (OPTIONAL, Adults Only): A needle muscle biopsy will be obtained twice during the study on up to 20 adults who voluntarily comply with this procedure at 6 months and 12 months into the study. An unblinded researcher, independent of [name] research team, will allocate an approximately equal number of subjects from each arm of the study based on the randomization scheme created for the entire study in advance by the NIH pharmacy for muscle biopsy: approximately 10 subjects from the intervention arm will be biopsied, approximately 10 subjects from the placebo arm will be biopsied. An outside muscle biopsy performed by the participants' local providers in the six months prior to the study 6-month time point will also be acceptable, to reduce the number of invasive procedures.

This muscle biopsy will be performed on the vastus lateralis or tibialis anterior muscle. After skin preparation using povidone-iodine or equivalent antiseptic, the skin and subcutaneous tissues will be anesthetized with 7-10 ml of 1% lidocaine without epinephrine. For side-cut biopsy needles (known as Bergstrom or UCHL needles) a 3mm incision will be made in the skin and muscle fascia, and muscle tissue will be obtained with 1 to 3 successful passes of the biopsy needle. Successful passes are defined as passes which obtain any muscle tissue. Due to issues, such as fatty infiltration of muscle in RYR1-RM, one additional incision may be made to obtain muscle tissue. The total number of passes will be limited to 6. Biopsy specimens (5 to 40 mg)

[figure not shown]
will be frozen as 1 or 2 aliquots depending on tissue yield. The aliquots will be frozen in liquid nitrogen within 2 minutes of removal and stored at -80°C until use. If additional tissue is obtained, it will be prepared as primary muscle cells and/or cell lines. Patients will be evaluated on the last day of the study visit to ask about post-biopsy pain or complications. To minimize variance resulting from time of day or muscle activity, the biopsy will be performed at a similar time of day and after a similar schedule of activities in all subjects at both study visits. Participants will be provided with a “Needle Aspiration Muscle Biopsy Procedure Information Sheet” (Appendix I.) prior to their visit, which describes the pre-procedure medication restrictions, procedure details, and post-procedure care instructions. This muscle biopsy will not be performed in minors.

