If Grade 1 side effects are reported, we will monitor them by phone and/or email and keep them on the drug. If Grade 2 side effects are reported, we will discontinue drug until the side effect resolves and then resume administration with careful observation for reoccurrence. Please see Section 7 under “Steps Taken to Minimize Risks” for further details.

9. Outcome Measures

Outcome Measures	Aim 1=Oxidative Stress	Aim 2=Fatigability, Fatigue
Primary	urine 15-F2t-isoprostane	6MWT
Secondary	DCFH assay in muscle biopsy (6 and 12 months only), blood GSH	Timed function tests; Biodex; PROMIS, FACIT, MFI, MRI, MFM, NeuroQoL scales, Myotools
Exploratory	Anaerobic threshold, NIRS; secreted ER calcium monitoring proteins (SERCaMPs) assay in blood and muscle	CPET, EIM, salivary FBI, melatonin, cortisol and DHEA; QoL qualitative interview

Aim 1

Blood and urine samples will be collected **at each visit**. Samples will be analyzed at NIH or shipped to [name] for urine isoprostane analysis at the Vanderbilt University Ecosinoid Core Facility. De-identified blood samples will also be shipped to Emory University to assay glutathione via mass spectrometry. Needle muscle biopsy will be performed at six and twelve months on up to 20 willing adult participants only.

GSH: Mass spectrometry, fluorescent, and colorimetric assays will be used to measure levels of reduced (GSH) and oxidized (GSSG) glutathione in plasma and whole blood to observe changes in oxidative stress. These assays include deproteinization, derivatization, and/or catalytic reactions.

DCFH: As in the preliminary studies above, DCFH will be used on participant muscle biopsies to analyze intracellular oxidant activity [H2DCFDA (H2-DCF, DCF)].

15-isoprostane-F2: Urine will be assayed for 15-isoprostane-F2, which is formed when arachidonic acid reacts with ROS. A validated GC-MS/MS method will be used to quantify 14-isoprostane-F2.

Anaerobic threshold: Anaerobic threshold and time to anaerobic threshold will be extrapolated from data obtained during CPET.

NIRS: Percentage of local muscle oxygen and oxygen consumption as determined by tissue oxygen index (TOI) and hemoglobin.

SERCaMPs: Measurement of protein level of *Gaussia* luciferase-based secreted ER calcium-monitoring protein (SERCaMP) in blood, primary muscle cells and/or cell lines. (Hendersen et al. 2015)

Aim 2

All procedures for Aim 2 will be performed at the NIH Clinical Center **at each visit**.

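### A local provider's biopsy may serve as the pre-treatment muscle sample without the study's handling conditions, which biases the within-patient and patient-versus-healthy DCFH comparisons and adds noise to the randomised one

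*Protocol*

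**What the plan says.** Protocol Section 4d (Muscle biopsy) plans a needle biopsy "obtained twice during the study on up to 20 adults who voluntarily comply with this procedure at 6 months and 12 months", about 10 per arm. The procedure is controlled. Freezing is timed: "The aliquots will be frozen in liquid nitrogen within 2 minutes of removal", followed by storage at -80°C. To limit variance, "the biopsy will be performed at a similar time of day and after a similar schedule of activities in all subjects at both study visits". Section 3c ties the pre-biopsy medication restrictions to the second and third visits.

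The same paragraph of Section 4d that sets the timing also states that an outside biopsy from "local providers in the six months prior to the study 6-month time point will also be acceptable, to reduce the number of invasive procedures". The reason given is burden on participants. No condition on muscle, technique, freezing, storage, time of day or prior activity is attached. The month-12 biopsy has no such option.

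On the muscle, Section 4d says: "This muscle biopsy will be performed on the vastus lateralis or tibialis anterior muscle". It does not require the same muscle at both visits.

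The Section 9 table lists, as a secondary Aim 1 outcome, "DCFH assay in muscle biopsy (6 and 12 months only"), so month 6 supplies the only pre-treatment value. Three analyses can use it:
- the comparison with each patient's own baseline (Protocol Section 2, Aim 1; paired t test in Section 10a);
- the comparison of month-6 DCF fluorescence with healthy individuals, where possible (SAP, Secondary Outcome Measures, Natural History Phase, Aim 1);
- the month-12 general linear model, NAC versus placebo, adjusted for baseline value (SAP, secondary outcomes, Intervention phase analyses).

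The SAP names no biopsy-source or muscle variable, no rule for outside tissue and no sensitivity analysis for it.

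**The concern.** The plan identifies sources of variance in the biopsy, controls them, and then exempts one side of the pre/post pair. Only the pre-treatment sample can come from outside, so a systematic difference between outside and study tissue does not cancel within a patient. It would appear as change under treatment or, at month 6, as a difference between patients and healthy individuals. An outside sample may also be up to six months older than the sample it replaces.

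The muscle is a separate gap. A pair taken entirely under the study procedure can still compare vastus lateralis with tibialis anterior.

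At stake is the reading of one mechanistic secondary outcome in a small subset. Neither primary outcome is affected.

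**Working it through.** **Plan's own figures.** The documents give no sample size or power for DCFH, no count of outside biopsies and no estimate of an offset. The one sample-size calculation with stated inputs (Section 10b: glutathione, delta 1.7, SDs 2.34 and 2.80, two-sided alpha 0.05, 80% power) reproduces. Satterthwaite t power is 79.8% at 37 per group and 80.9% at 38, so 38 per group. It has no bearing on DCFH.

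**Assumptions.** k of 10 patients in an arm have an outside month-6 sample, which differs from study tissue by b SD, with b from 0.5 to 1.5. For change scores the unit is the SD of the change. For the linear model and the healthy comparison it is the SD of a single measurement. The two units are equal when the month-6 to month-12 correlation is 0.5, because SD(change) = sqrt(2(1 − r)) × SD.

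**1. Within-patient change, n = 10, no true change.** Bias = k × b / 10. For k = 3: 0.3 × 0.5 = 0.15 SD, up to 0.3 × 1.5 = 0.45 SD. Simulated type I error of the paired t test (100,000 runs, nominal 5%):

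| k | b = 0.5 | b = 1.0 | b = 1.5 |
|---|---|---|---|
| 2 | 5.5% | 6.6% | 7.7% |
| 3 | 6.4% | 10.0% | 13.2% |
| 5 | 9.8% | 21.6% | 35.5% |

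Randomisation gives no protection here.

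**2. Month-6 patients versus healthy.** Bias = share of outside samples × b. With 3 of 20: 0.15 × 0.5 = 0.075 SD, up to 0.15 × 1.5 = 0.225 SD. Randomisation does not help here either.

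**3. Randomised month-12 model adjusted for baseline.** The outcome is always a study sample; only the covariate is contaminated. The bias is therefore the fitted slope times the between-arm difference in mean contamination. For 3 of 10 versus 0 of 10 that difference is 0.3b. The slope is roughly r / (1 + 0.105b²), where 0.105 is half of 0.3 × 0.7, the extra covariate variance averaged over the arms.
- r = 0.3, b = 0.5: 0.3 / 1.026 × 0.15 = 0.044 SD.
- r = 0.7, b = 1.5: 0.7 / 1.236 × 0.45 = 0.255 SD.

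Simulation (20,000 runs per setting) gives 0.04 to 0.25 SD, with a false-positive rate of about 5% to 9%. For scale, the unadjusted standard error of a difference between two arms of 10 is sqrt(2/10) = 0.447 SD.

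**4. How likely is that split?** If 3 of 20 patients used the option, all three fall in one arm with probability 2 × C(10,3) / C(20,3) = 240 / 1140 = 21%.

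**5. Balanced use.** With 3 outside samples in each arm there is no between-arm bias, and in a t test on the change type I error stays below 5%. Power for a 1.32 SD effect falls from 80% to 78.5%, 73.4% and 64.7% for b = 0.5, 1.0 and 1.5. So the cost is precision.

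**The case against.** The strongest objection is that the randomised comparison is largely safe. An outside biopsy precedes the 6-month time point and patients are randomised at the end of that visit (Section 4a), so use of the option cannot depend on treatment. A reader might infer that randomisation fails here, or that the treatment comparison is biased by the full 0.15 to 0.45 SD. The documents support neither. Expected between-arm bias is zero, and the SAP specifies a baseline-adjusted month-12 model rather than a change score, which shrinks any chance imbalance by the slope. This stands.

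Other objections also stand in part:
- Section 4d does not say that outside tissue would be assayed for DCFH. The link is an inference from Section 9. Nor does it say that outside samples breached the study conditions; it is silent.
- The paired t test comes from Protocol Section 10a. The SAP's intervention-phase section lists no paired month-6 to month-12 test for secondary outcomes.
- The SAP leaves its confounder list open, so source could be added to the model. But it is not pre-specified, and the SAP names no variable to carry it.
- Collection is over. Section 10b says the study is being closed to data analysis and the SAP refers to locked files, so rewriting the biopsy procedure would change nothing. Dropping patients from the main model would also sit badly with the SAP's intent-to-treat heading, because the SAP imputes only missing month-12 data and has no rule for a discarded month-6 value.

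None of this protects the within-patient or the patient-versus-healthy comparison.

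**Conclusion.** The point holds for the two non-randomised comparisons. Any source offset biases the within-patient DCFH change and the month-6 comparison with healthy individuals directly, in proportion to the share of outside samples. The randomised month-12 model has zero expected bias and mainly loses precision. Under the assumed 3-versus-0 split, offset of 0.5 to 1.5 SD and correlation of 0.3 to 0.7, it would be off by about 0.04 to 0.25 SD. That split is unfavourable: it has a 21% chance even if three patients used the option.

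All these sizes rest on an assumed count and an assumed offset. The number of outside samples is not given and may be zero, in which case only the muscle question remains. A reader should not conclude that the trial's treatment comparison is compromised. DCFH is one secondary outcome in an optional subset of up to 20 adults, with a detectable difference of about 1.32 SD at 10 per arm even with uniform samples.

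**What to change.** Make the change in the SAP:
- Add a flag for the source (study procedure or outside) and the muscle of each biopsy.
- Base the paired DCF change on pairs in which both samples were taken under the study procedure from the same muscle.
- Base the month-6 comparison with healthy individuals on study-procedure samples only. The healthy volunteers' procedures in Section 4d include no biopsy, so the source of the healthy values should be stated too.
- Keep every randomised, biopsied patient in the main month-12 model, and add a sensitivity analysis that excludes mixed-source and mixed-muscle pairs.
- Report the number of such pairs by arm. If there were no outside samples, one sentence closes that part.

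Cost: two flag columns and a few lines of text. A few pairs are lost from the paired analysis. In the sensitivity analysis the between-arm difference detectable with 80% power (two-sample t test) rises from about 1.32 SD at 10 per arm to 1.41 SD at 9 or 1.51 SD at 8.
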